4. STUDY POPULATION

4.1 Population (base)

The base population consists of community-dwelling elderly individuals aged 60–75 years residing in Jakarta, Indonesia, who participate in community programs managed by the School of Medicine and Health Sciences at Atma Jaya Catholic University of Indonesia and the Archdiocese of Jakarta. Additionally, healthy children aged 5–8 years from cooperating orphanages (Panti Asuhan) in the Jakarta area are recruited exclusively for the intergenerational activities in the intervention arm.

4.2 Inclusion criteria

For elderly participants:

- Aged 60–75 years
- Meet diagnostic criteria for physio-cognitive decline syndrome (PCDS): gait speed <1.0 m/s and/or hand grip strength <28 kg (men) or <18 kg (women), and MoCA-Ina score 22–26
- Instrumental Activities of Daily Living (IADL) score >5

- Able to understand and follow instructions adequately
- Willing to participate and provide written informed consent

For child participants (intervention group only):

- Aged 5–8 years
- In good health and cooperative
- Able to understand and follow instructions
- Written permission obtained from orphanage management

4.3 Exclusion criteria

For elderly participants:

- Presence of disability or dementia
- Depression or other mental health disorders
- Total immobility
- Acute illness at screening (e.g., pneumonia, acute arthritis with VAS >6/10, acute stroke, acute myocardial infarction, uncontrolled hypertension $\geq 180/100$ mmHg, acute COPD exacerbation)
- Uncontrolled chronic lung or heart disease
- Hemodynamic instability or hypotension (<90/60 mmHg) at screening
- Recent hospitalization or major surgery within 2 weeks prior to screening
- Illiteracy (unable to read/write)
- Unwilling to participate

For child participants:

- History of chronic illness, behavioral disorders, intellectual disability, or psychiatric conditions
- History of sensory integration therapy, speech therapy, or child psychological therapy
- Unwilling to complete the study

4.4 Screening

Potential elderly participants are identified consecutively through community programs. Screening involves:

- Medical history and informed consent
- MoCA-Ina cognitive assessment
- Hand grip strength (dominant hand, best of 3 trials)
- 6-meter gait speed test (average of 2 trials)
- IADL assessment
- Basic physical examination and vital signs to rule out acute/uncontrolled conditions

Eligible elderly are then randomized. Child participants are selected in collaboration with orphanage management based on age, health status, cooperation, and written permission.

4.5 Sample size calculation

The sample size was calculated to detect clinically meaningful differences between the intervention and control groups in key outcome measures, including handgrip strength, gait speed, cognitive function (MoCA-Ina score), health-related quality of life (SF-12), and serum mature brain-derived neurotrophic factor (mBDNF) levels.

Sample size estimation was performed using the formula for comparison of two independent means, with a two-sided significance level (α) of 5% and a statistical power ($1-\beta$) of 80%. The standard deviation and expected mean differences for each outcome were derived from previously published studies involving older adults, as no prior studies have specifically evaluated SHP-based interventions or their combination with structured physical exercise.

Based on these calculations, the required sample sizes for individual outcome parameters ranged from 9 to 42 participants per group. Considering the largest estimated sample size requirement and allowing for potential dropouts, the minimum required sample size for this randomized controlled trial was determined to be 100 older adult participants, with **50 participants allocated to each group (intervention and control)**.

This sample size is considered sufficient to evaluate the primary and secondary outcomes of the study and to ensure adequate statistical power while accounting for potential attrition during the study period.

5. TREATMENT OF SUBJECTS

Subjects will be randomly assigned to one of two groups: structured physical exercise followed by a social heterochronic parabiosis (SHP)-based intervention (intervention group) or usual care only (control group). Randomization will be computer-generated using a block-permuted randomization method with variable block sizes of four. The randomization list will be held by an independent third party (staff of the Department of Internal Medicine, School of Medicine and Health Sciences, Atma Jaya Catholic University of Indonesia) who is not involved in the research team. Both the investigators and the participants will be blinded to group allocation.

5.1 Investigational product/treatment

All participants (both arms) receive standardized nutritional education as a base intervention:

- Two personalized nutritional consultations via Zoom tele-conference with a certified dietitian (week 1 and week 11), focusing on balanced nutrition tailored to elderly needs.
- Five educational e-flyers on nutrition, physical activity recommendations for the elderly, and related topics (sent via mobile device at weeks 3, 5, 7, 13, and 15).

Intervention group (n=50 elderly + 50 children): In addition to nutritional education, participants receive a sequential multimodal intervention:

1. Structured physical exercise (weeks 1–12):

- Chair-exercise using the Indonesian Osteoporosis Association (PEROSI) protocol, adapted for tele-exercise.
- Sessions: 60 minutes duration, consisting of 10 min warm-up (light aerobic + flexibility), 30 min core (moderate aerobic, strength, balance), 5–10 min cool-down (light aerobic + stretching).
- Frequency progression: 1 session/week (weeks 1–2), 2 sessions/week (weeks 3–6), 3 sessions/week (weeks 7–12).
- Delivery: Online (tele-exercise) supervised by 1 certified PEROSI instructor and assisted by 1 research team member.
- Safety: Pre-session physical condition check; exercise termination based on Borg scale and American College of Sport Medicine (ACSM) guidelines for the elderly.

2. Social Heterochronic Parabiosis (SHP)-based intergenerational intervention (weeks 13–16):

- Group-based direct interaction: Each elderly participant paired 1:1 with one child participant (aged 5–8 years).

- Sessions: 8 total (2 sessions/week, 45 minutes each) conducted in-person at selected orphanages.
- Content: Educational and interactive activities using “Ayo Minum Air” (AMIR) materials from Indonesian Hydration Working Group (comic reading, simple gymnastics demonstration, educational games promoting hydration and healthy lifestyle).
- Organization: Elderly divided into 5 groups (10 elderly each); scheduled visits with research team accompaniment; facilities prepared for conducive interaction (seating, materials, spacing).
- Preparation: Training of Trainers (ToT) for elderly participants and research team during weeks 11–12 (3 sessions, 30 min each, outside exercise schedule).

Control Group

Participants in the control group will receive usual care according to existing community health services. They will not participate in the structured exercise or SHP-based intergenerational activities during the study period. However, they will continue to receive standard health education and routine activities available within their respective community settings.

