9. STATISTICAL ANALYSIS

All collected data will be initially recorded on research case report forms (CRFs) and subsequently transferred to secure electronic storage for data cleaning, coding, and verification. Descriptive data and analytical results will be presented in narrative text, tables, or figures as appropriate.

Normality of data distribution will be assessed using the Kolmogorov-Smirnov or Shapiro-Wilk test ($p > 0.05$ indicates normal distribution). Normally distributed continuous data will be presented as mean \pm standard deviation (SD); non-normally distributed data as median with minimum-maximum range. Categorical data will be presented as frequencies and percentages. Statistical significance will be set at $p < 0.05$. All analyses will be performed using SPSS version 20 software.

Primary analyses will be conducted on the per-protocol (PP) population, excluding drop-out subjects. Between-group comparisons of changes in study outcomes (hand grip strength, gait speed, MoCA-Ina score, serum mBDNF levels, and health-related quality of life) will use unpaired t-tests (parametric) or Mann-Whitney U tests (non-parametric), selected based on normality test results.

Correlations between serum mBDNF levels and MoCA-Ina score, hand grip strength, and gait speed will be evaluated using Pearson correlation (for normally distributed variables) or Spearman correlation (for non-normally distributed variables), according to normality assessment of each variable.

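### In weeks 13–16 the intervention arm is treated in five groups of ten, but Section 9 plans only tests that assume independent participants; if SHP groups differ in effect or share conditions, the planned standard error is too small

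*Combined protocol and SAP*

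**What the plan says.** Section 5.1 of the protocol describes the last phase of the intervention as "Social Heterochronic Parabiosis (SHP)-based intergenerational intervention (weeks 13–16", delivered as "Group-based direct interaction" at orphanages: eight sessions of 45 minutes. Each older adult is paired with one child, and for organisation the plan has "Elderly divided into 5 groups (10 elderly each", visiting on a schedule with the research team. The preceding 12 weeks of online exercise are "supervised by 1 certified PEROSI instructor and assisted by 1 research team member"; how participants are grouped for those sessions is not stated. Of controls the same section says: "They will not participate in the structured exercise or SHP-based intergenerational activities during the study period".

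Sections 7.1.1 and 7.1.2 define the outcomes as changes from baseline to week 16, the end of the SHP phase. On sample size, Section 4.5 states: "Sample size estimation was performed using the formula for comparison of two independent means". Section 9 says that between-group comparisons of hand grip, gait speed, MoCA-Ina, mBDNF and quality of life "will use unpaired t-tests (parametric) or Mann-Whitney U tests (non-parametric), selected based on normality test results". The document mentions no intraclass correlation, design effect, random effect for group or orphanage, or cluster-robust standard error.

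**The concern.** This is a partially nested design: one arm is treated in groups for part of the trial and the other is not. Individual randomisation makes the arms comparable at entry, but it does not prevent correlation that arises later through shared sessions. If some SHP groups go better than others, members of a group have correlated changes, and the mean of the intervention arm varies more than 50 independent people would imply. Neither planned test sees that extra variation.

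A group effect is plausible. Section 12.1 itself anticipates interactions that are not harmonious and difficulties in coordinating several orphanages. At stake are the stated 5% level and the width of any confidence interval that is reported. If group membership is not recorded, the dependence may also be impossible to examine afterwards.

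**Working it through.** **Inputs from the protocol.** Five SHP groups of 10 and no trial groups for controls (Section 5.1); two-sided alpha 5%, power 80%, largest requirement 42 per group, 50 per group planned (Section 4.5); dropout up to 15% (Section 7.6). The ICC is an assumption, taken over the range 0 to 0.20.

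**The plan's own figure.** 42 / (1 − 0.15) = 49.4, which rounds up to 50 per arm, so the stated size reproduces. The effect size behind 42 is not given. Solving n = 2(1.960 + 0.842)² / d² for n = 42 gives d ≈ 0.61, which is used below.

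**How much is grouped.** Exercise: 2×1 + 4×2 + 6×3 = 28 sessions of 60 minutes = 28 hours. SHP: 8 × 45 minutes = 6 hours. So about 6 of 34 contact hours (18%) are stated to be in the five groups.

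**Effect on the standard error.** With total variance 1 in each arm and correlation only in the intervention arm:
- design effect DE = 1 + (10 − 1) × ICC
- true SE / planned SE = √[(DE + 1) / 2]
- type I error ≈ 2 × [1 − Φ(1.96 / ratio)]

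Example at ICC 0.05: DE = 1.45, ratio = √(2.45 / 2) = 1.107, type I error ≈ 2 × [1 − Φ(1.771)] = 7.7%.

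The simulated columns use 100,000 trials per ICC, five groups of 10 against 50 independent controls. The Welch test compares the five group means with the individual controls, using Satterthwaite degrees of freedom.

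| Assumed ICC | DE | SE ratio | t-test type I, formula | t-test type I, simulated | Welch type I, simulated | Welch power, d = 0.61 |
|---|---|---|---|---|---|---|
| 0 | 1.00 | 1.000 | 5.0% | 5.0% | 5.2% | 81% |
| 0.01 | 1.09 | 1.022 | 5.5% | 5.5% | 5.2% | 79% |
| 0.02 | 1.18 | 1.044 | 6.0% | 6.0% | 5.3% | 76% |
| 0.05 | 1.45 | 1.107 | 7.7% | 7.8% | 5.4% | 71% |
| 0.10 | 1.90 | 1.204 | 10.4% | 10.4% | 5.5% | 62% |
| 0.20 | 2.80 | 1.378 | 15.5% | 15.7% | 5.6% | 49% |

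The Mann-Whitney test does not escape: in 8,000 simulated trials it rejected 7.2% of the time at ICC 0.05 and 9.8% at 0.10.

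**After dropout.** Section 9 makes the per-protocol population primary. With about 42 completers per arm (8.4 per group), the formula gives type I errors of 5.9%, 7.2% and 9.4% at ICC 0.02, 0.05 and 0.10. Simulated power of the Welch test at d = 0.61 is about 72–73% at ICC 0 and 64–65% at ICC 0.05. The unclustered t-test at ICC 0 has about 78–79% (80% by the normal approximation).

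**The case against.** The strongest case against has four parts.

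*Little of the treatment is grouped.* Only about 18% of contact time is stated to be in groups, at the end of a programme whose outcomes run from week 0. The interaction is largely between an older adult and a paired child. Fixed membership is implied rather than stated, and nothing says that each group has its own staff; one team serving all five would add no between-group staff effect. All of this stands. It makes a small ICC plausible, and at 0.01 to 0.02 the error rate is only 5.5% to 6.0%.

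*Under the strict null there is nothing to inflate.* If the intervention affects nobody, group delivery induces no correlation and individual randomisation keeps the t-test at about 5%. That is right. The inflation needs groups that differ in effect while averaging to zero, or groups that share conditions such as measurement circumstances, which the documents do not describe. A reader might infer that every week-16 comparison will exceed 5%. The documents do not support that: it depends on a non-zero ICC, and Section 9 names no test at all for frailty status, a primary endpoint.

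*The remedy costs power.* This also stands. After the planned dropout, the group-mean test falls below 80% even with no clustering. A reader might infer that it must replace the primary test; that is a debatable trade-off, not something the documents compel.

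*Five groups are too few, and the ICC is unknown.* This part does not stand. The group-mean test needs no assumed ICC, and with five groups its small-sample degrees of freedom keep it at 5.2–5.6%. A mixed model behaves differently: its group variance is estimated as zero in about 58% of trials at ICC 0 and 37% at ICC 0.05, although it still held its level (3.7–4.6%).

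**Conclusion.** The point holds in conditional form. The SHP phase creates five groups in one arm only, and the planned tests have no means of reflecting a shared group effect. If there is one, the planned standard error is too small by a factor of 1.04, 1.11 and 1.20 at ICC 0.02, 0.05 and 0.10, and the nominal 5% test runs at about 6%, 8% and 10%. At ICC 0.01 or below the problem is slight. These figures assume equal total variances, fixed membership in groups of 10, and an ICC that the documents do not give.

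The point covers mBDNF and the continuous secondary outcomes. mBDNF, read by blinded analysts, may cluster less than MoCA-Ina or SF-12, but that too is an assumption. Section 9 does not mention confidence intervals; any that are reported from an unclustered analysis would be too narrow in the same way.

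One could read the grouping as covering the whole intervention. The documents state it only for weeks 13–16. If the single exercise instructor has an effect, it is confounded with the arm, and no clustering adjustment can remove it.

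**What to change.** 1. Record each intervention participant's SHP group and orphanage on the case report form, and state in Section 5.1 whether membership is fixed.
2. Prespecify in Section 9 a partially nested analysis of mBDNF and the continuous secondary outcomes. It should have a random group effect in the intervention arm only, separate arm variances and Satterthwaite degrees of freedom. The alternative is Welch's test of the five group means against individual controls. Choose one in advance, since the two can differ, more so when groups become unequal after dropout.
3. Report it beside the planned test, at least as a sensitivity analysis. State that a significant unclustered result which it does not support will be interpreted cautiously.
4. Report the estimated ICC with its imprecision, which will be large with five groups.

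The cost is two recorded variables and some wording, plus lower power for the added analysis. For d = 0.61 at 50 per arm, the Welch test has about 80% at ICC 0 and 70% at ICC 0.05, against about 86% for the unclustered test at ICC 0. With about 42 completers per arm the shortfall is about 6 points at ICC 0. If the sponsor prefers to make the clustered test primary, the sample size in Section 4.5 should be revisited.

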5.2 Use of co-intervention (if applicable)

Co-interventions are minimized and monitored:

- Routine medications and medical care are permitted and recorded.
- Additional structured exercise or intergenerational programs outside the study are not allowed during the 16-week period and will be queried at follow-up visits.
- Both arms receive identical monitoring (phone counseling 2–3 times/month) to encourage adherence and prevent dropout.

5.3 Escape medication (if applicable)

Not applicable. This is a non-pharmacological intervention study; no escape medication is provided. In case of clinical deterioration or acute illness, participants are withdrawn and referred for standard medical care.

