3. STUDY DESIGN

This is a single-center, randomized, open-label (unblinded), parallel-group controlled clinical trial evaluating the efficacy of a sequential multimodal intervention (structured physical exercise followed by SHP-based intergenerational activities) compared to nutritional education alone in community-dwelling elderly aged 60–75 years with physio-cognitive decline syndrome (PCDS).

The study duration per participant is 16 weeks, consisting of:

- Baseline assessment (week 0)
- Intervention period: 12 weeks of chair-exercise + 4 weeks of intergenerational activities (intervention arm) or continued education (control arm)
- Intermediate assessment (end of week 12)
- Final assessment (end of week 16)

Participants are randomized in a 1:1 ratio into two arms:

- Intervention arm (n=50): Nutritional education + 12 weeks structured chair-based exercise (PEROSI protocol, progressive frequency from 1 to 3 sessions/week, 60 minutes/session, supervised online) followed sequentially by 4 weeks SHP-based intergenerational activities (8 sessions, 2x/week, 45 minutes/session, paired 1:1 elderly-child using AMIR educational materials at selected orphanages).
- Control arm (n=50): Nutritional education only (2 personalized dietitian tele-conferences at weeks 1 and 11; 5 educational e-flyers at weeks 3, 5, 7, 13, and 15).

Randomization is computer-generated using permuted block randomization (block size 4), stratified if necessary, with allocation concealment managed by an independent third party. Blinding of participants and instructors is not feasible due to the nature of the behavioral interventions; however, outcome assessors for laboratory analyses (mBDNF) are blinded to group allocation where possible.

The trial follows intention-to-treat principles with per-protocol sensitivity analysis. Recruitment targets consecutive eligible elderly from community programs under the School of Medicine and Health Sciences at Atma Jaya Catholic University of Indonesia and the Archdiocese of Jakarta. Child participants (aged 5–8 years, n=50) are recruited from cooperating orphanages exclusively for the intervention arm.

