7.5 Withdrawal of individual subjects

Participants (elderly or children via orphanage representative) may withdraw voluntarily at any time without providing reasons and without impact on routine care or relationship with researchers. Withdrawal is documented but no further study procedures performed unless consented for final assessment.

Investigator-initiated withdrawal occurs for:

- Development of exclusion criteria (e.g., new disability, dementia suspicion, uncontrolled chronic disease).
- Acute illness requiring hospitalization or prohibiting continuation (e.g., pneumonia, acute stroke, uncontrolled hypertension).
- Non-adherence (>3 consecutive missed exercise sessions or <85% overall intervention completion).
- Intolerable adverse events suspected related to intervention.

Withdrawn participants are encouraged to complete safety follow-up and/or final assessments for intention-to-treat analysis. All withdrawals are fully documented (reason, date, partial data

collected) and reported to Ethics Committee if related to safety. No replacement of withdrawn subjects.

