7.5.1 Drop out Criteria

Subjects are classified as drop-outs if they do not complete the study protocol through the final assessment (week 16) for any reason. Specific drop-out criteria include:

- Non-adherence to intervention: Failure to attend >3 consecutive structured exercise sessions (intervention arm) or $<85\%$ of total planned exercise sessions; failure to attend ≥ 2 intergenerational activity sessions or $<85\%$ overall attendance for SHP phase.
- Development of exclusion criteria during study: New onset of disability, suspected/confirmed dementia, depression (GDS-15 score indicating moderate-severe depression requiring intervention), total immobility, uncontrolled chronic disease, or hemodynamic instability.
- Acute illness or clinical worsening: Occurrence of acute conditions (e.g., pneumonia, acute arthritis with VAS $>6/10$, acute stroke, acute myocardial infarction, uncontrolled hypertension $\geq 180/100$ mmHg, acute COPD exacerbation) requiring hospitalization or prohibiting continuation.
- Adverse events suspected related to intervention: Intolerable or serious symptoms (e.g., persistent severe fatigue, muscle pain, dizziness, fall during exercise, significant emotional distress during intergenerational activities) leading to investigator decision for withdrawal.
- Voluntary withdrawal: Subject (or orphanage representative for children) requests discontinuation for any personal reason (e.g., lack of time, loss of motivation, transportation difficulties).
- Loss to follow-up: Inability to contact subject despite ≥ 3 attempts via phone/WhatsApp over 2 weeks, or permanent relocation outside study area.
- Death: Any mortality during study period (reported immediately as serious adverse event).

All drop-outs are documented in detail (date, reason, last completed assessment/procedure) on the case report form and in the trial master file.

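### Section 9 makes the per-protocol set primary and excludes drop-outs, against the intention-to-treat principle in section 3; the unqualified withdrawal sentence in 5.3 adds to this in a minor way

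*Combined protocol and SAP*

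**What the plan says.** On the analysis set, the combined protocol and SAP gives two answers.

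- Section 3 (Study Design): "The trial follows intention-to-treat principles with per-protocol sensitivity analysis".
- Section 9 (Statistical Analysis): "Primary analyses will be conducted on the per-protocol (PP) population, excluding drop-out subjects". No intention-to-treat analysis is described there, as primary or otherwise.

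On who counts as a drop-out, 7.5.1 says: "Subjects are classified as drop-outs if they do not complete the study protocol through the final assessment (week 16) for any reason". Its specific criteria include attendance (for example "Failure to attend >3 consecutive structured exercise sessions (intervention arm"), new exclusion criteria, acute illness, adverse events, voluntary withdrawal and loss to follow-up.

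On data after withdrawal, 7.5 says: "Withdrawn participants are encouraged to complete safety follow-up and/or final assessments for intention-to-treat analysis". Section 7.7 repeats this.

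On illness, 5.3 says: "In case of clinical deterioration or acute illness, participants are withdrawn and referred for standard medical care". Section 7.5 is narrower: "Acute illness requiring hospitalization or prohibiting continuation". Section 7.5.1 sets the same limit on its acute-illness item: "requiring hospitalization or prohibiting continuation".

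**The concern.** Randomisation makes the two groups comparable as allocated. Removing participants afterwards, for reasons that may relate to health, motivation or response, can undo that. Three features of this trial make the exclusion more than a formality.

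- The staff who decide on withdrawal know the arm. Section 7.2 states that the research team cannot be blinded. Section 5 says the investigators are blinded, but anyone running the sessions can see who attends them.
- The rules differ by arm. The attendance criteria in 7.5.1 concern exercise and intergenerational sessions, which controls do not have. Section 7.3.8 logs nutritional education in both arms but sets no threshold for it.
- The plan already asks for the data that would avoid the problem, and section 9 then does not use them.

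Section 5.3 matters only as an addition. A participant with a brief illness who could resume is withdrawn under its literal wording and retained under 7.5. No section says which rule governs.

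**Working it through.** **1. Path from withdrawal to exclusion.** Section 7.5.1 lists attendance failure and illness above the hospitalisation or inability-to-continue threshold as drop-out criteria, and section 9 excludes drop-outs. For these participants the path is explicit. For someone withdrawn only under 5.3 for a brief illness it is likely but not stated: that person has not completed the study protocol, but the text does not say how attendance at week 16 would change the classification.

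**2. Size of the exclusion at the planned rate.** Inputs: 42 per group for the most demanding outcome (4.5) and drop-out of up to 15% (7.6). The plan's own figure reproduces: 42 / (1 − 0.15) = 49.4, rounded up to 50 per group. At that rate, 0.15 × 50 = 7.5 per arm, or 15 of 100 randomised, fall outside the primary analysis.

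**3. Why the bias cannot be sized.** If a share p of an arm is excluded, the mean of those retained differs from the mean of the whole arm by p × (retained mean − excluded mean). At p = 0.15 this is 0.15 times that gap. The bias in the comparison is this quantity in the intervention arm minus the same quantity in the control arm. The documents give neither the gap nor the split of drop-outs by arm, so neither sign nor size follows.

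**4. What 5.3 adds in the intervention arm.** Session schedule (5.1): 2×1 + 4×2 + 6×3 = 28 exercise sessions, then 8 intergenerational sessions at 2 per week. More than 3 consecutive misses means 4. Without 5.3, continuous absence makes a participant a drop-out after:

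- about 3 weeks if it starts in week 1 (1 + 1 + 2 = 4 sessions);
- about 2 weeks in weeks 3–6 (4/2);
- about 1.3 weeks in weeks 7–12 (4/3);
- at most about 1 week in the intergenerational phase (2 missed sessions at 2 per week).

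These durations assume no earlier misses. The 85% rule is cumulative: 0.85 × 28 = 23.8, so 24 sessions are needed and a fifth miss fails (23/28 = 82%). Earlier absences therefore shorten the intervals. In this arm 5.3 adds only illness shorter than these intervals. In the control arm, which has no session rule, it adds any noticed illness below the 7.5 threshold.

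**5. Power.** For two means at two-sided 5%, normal approximation, 42 per arm at 80% power implies a standardised difference of 2.80 × √(2/42) = 0.611. With n per arm, power is Φ(0.611 × √(n/2) − 1.96):

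- n = 42.5 (the planned 15% loss): 80.5%;
- n = 40 (assumed loss of 10 per arm): Φ(0.77) = 78%;
- n = 38 (assumed loss of 12 per arm): Φ(0.70) = 76%.

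This applies only to the most demanding outcome, which 4.5 does not name. The other outcomes need as few as 9 per group.

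**The case against.** The best case for the plan concerns 5.3. The sentence closes a section marked not applicable. Its terms closely match the acute-illness item in 7.5.1, which supplies the threshold. The examples of acute illness in 4.3, 7.5 and 7.5.1 are mostly serious conditions, and 8.1.1 manages mild events by rest and session adjustment. This stands: the sentence is probably loose wording, and the narrower rule is probably meant. A reader might infer that the plan orders immediate withdrawal for every minor illness, or that worsening on frailty or cognition is itself a ground for removal. The documents do not support either reading. Section 5.3 does not say so, and the dedicated sections point the other way. What remains is an operative sentence with no threshold and no cross-reference.

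It can also be said that the harm comes from section 9 and would exist without 5.3. That is right, and it is why section 9 is the main point here. Correcting 5.3 alone would leave every other drop-out excluded.

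Finally, 7.5 and 7.7 already provide for assessment after withdrawal, and participants are free to decline it. That reduces how much needs changing, but it does not help while section 9 leaves the resulting data unused.

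**Conclusion.** Sections 3 and 9 contradict each other on the primary analysis set, and section 9 contains the weaker choice. As written, up to 15 of 100 randomised participants would be excluded at the plan's own drop-out rate, for any reason, in an open-label trial whose attendance criteria apply to one arm's sessions. Section 5.3 is a minor contributor: a loose sentence which, if followed, would create avoidable withdrawals that are likely to be classed as drop-outs.

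Two stronger conclusions are tempting and not supported. One is that the exclusions favour the intervention: the direction depends on outcomes among those excluded and on their split by arm, and the documents give neither. The other is that the trial becomes underpowered: 76–78% for the most demanding outcome rests on assumed losses of 10 or 12 per arm, since no illness rate is given. The point is the exclusion after randomisation itself. It should be corrected, and the correction is easy.

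**What to change.** 1. **Section 9:** make the primary analysis include all randomised participants in their assigned arm, using every available week-16 assessment whatever the reason for withdrawal or drop-out (illness, attendance or other). Keep the per-protocol set, defined by the 85% attendance rule in 7.3.8, as the sensitivity analysis, as section 3 says. Restoring only the illness withdrawals would not do: the set would be neither intention-to-treat nor per-protocol, and attendance drop-outs would still be lost from the intervention arm.
2. **Section 5.3:** replace the sentence with: *Participants with acute illness are referred for standard medical care; withdrawal follows the criterion in 7.5.*
3. **Sections 7.5 and 7.5.1:** state that investigator withdrawal or drop-out classification, including for non-adherence, stops the intervention but not the planned week-16 assessment, unless the participant withdraws consent.

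The cost is wording; no new visit is needed. Including participants who did not complete the intervention may dilute the estimate. With all 50 per arm assessed, a dilution of up to 1 − √(42/50) = 8% still leaves 80% power for the most demanding outcome. In an extreme case, where 15% of the intervention arm gains nothing, power would be Φ(0.85 × 0.611 × √25 − 1.96) = Φ(0.64), about 74%. Participants who decline week 16 remain missing, and their number and reasons should be reported by arm.
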